1. SYNOPSIS

Study Title	Investigation of somatosensory predictors of response to pregabalin in painful chemotherapy-induced peripheral neuropathy (CIPN).
Objective	In a prospective, randomized, double-blind, cross-over study, to determine the correlation between mechanical pain threshold (MPT) at baseline and analgesic response to 4-week treatment with pregabalin vs. placebo in patients with painful CIPN.
Hypothesis	Increased mechanical hypersensitivity to pinprick (lower mechanical pain threshold (MPT)) corresponds to better analgesic response to pregabalin treatment in painful CIPN.
Study Period	Planned enrollment duration: Approximately 18 months Planned study duration: 10 weeks per subject; 4 weeks duration per arm, with 2 weeks washout between the two treatments.
Number of Patients	35 evaluable patients with painful CIPN
Study Treatment	Oral pregabalin (or matching placebo) administered BID and titrated to individual response in a dose up to 600mg/day. In subjects with CrCL of 30-60 mL/min, the dose will be limited to 300mg/day.
Study Design	Prospective, randomized, double-blind, placebo-controlled, cross-over study.
Inclusion and Exclusion Criteria	
Inclusion criteria:
 
 1. Age >18 2. Distal symmetric pain distribution (both feet, with or without pain in hands). 3. The pain appeared during or up to 12 weeks after treatment with oxaliplatin, paclitaxel, docetaxel or any combination of these. 4. Score of 4 or more on DN4 neuropathic pain questionnaire 5. Pain duration > 2 months. 6. Patient report of average daily pain intensity in the last week >3 on 0-10 Numerical Rating Scale (NRS). 7. Women of childbearing potential and men must agree to use adequate contraception (hormonal or barrier method of birth control, abstinence) prior to study entry and for the duration of study participation. 8. Able and willing to sign an IRB-approved written informed consent. 
Exclusion criteria:
 
 1. Hypersensitivity to pregabalin. 2. Current treatment with pregabalin. 3. Current treatment with a vinca alkaloid (e.g. vincristine, vinblastine), or CIPN that may be associated with previous treatment with a vinca alkaloid. 4. History of diabetes mellitus or a neurological disorder with any

	
previous signs of distal symmetric polyneuropathy.
 
5. Moderate to severe renal failure ($\text{CrCL} < 30\text{mL/min}$, by Cockcroft-Gault formula).
 
6. ALT (SGPT) or AST (SGOT) > 3 times the upper limit of normal.
 
7. Planned surgeries or radiation treatment within 10 weeks following study inclusion.
 
8. Inability to complete pain self-report.
 
9. Pregnancy or lactation
 
10. Patients with seizure disorders treated with anticonvulsants
 
11. Current participation in a trial with another investigational agent unless co-enrollment is approved by the PIs of both studies.
 
12. Concomitant medication as follows:
 
 • Subjects treated with gabapentin or other anticonvulsant for neuropathic pain will be required to taper the medication and discontinue for at least 2 weeks prior to study initiation. • Patients on antidepressant treatment for pain or depression (TCAs, SSRI, SNRIs etc. will be allowed to continue their medications provided they have been on a stable dose for at least 4 weeks before study initiation. No dose regimen changes of antidepressants will be allowed during the study period. • Patients on around-the clock opioid treatment (including tramadol) will be allowed to continue their medication provided they have been on a stable dose for at least 4 weeks before study initiation. The maximum allowed dose of opioid will be equivalent to 60mg oral morphine sulphate. Patients with higher doses will be required to taper down their opioid dose to maximum 60mg oral morphine equivalent, and continue on stable dose for 4 weeks before enrollment in the study. PRN short-acting opioids for painful CIPN treatment will not be allowed. Patients receiving PRN short-acting opioids (with or without acetaminophen) for pain other than CIPN will be allowed up to 4 daily doses, with daily recording of analgesic consumption. • Treatment with NSAIDs will be discontinued at least 2 weeks before study initiation. However, low-dose aspirin ($\leq 325\text{mg/day}$) will be allowed.
Measurements	
Baseline sensory testing:
 
 1. Quantitative sensory testing (QST): Mechanical Pain Threshold, thermal detection and pain thresholds, mechanical detection threshold, pressure pain thresholds, temporal summation (TS), and conditioned pain modulation (CPM).

	
 2. Spontaneous pain at baseline on 0-10 Numerical Rating Scale (NRS); 3. Assessment of pain symptoms on Neuropathic Pain Symptom Inventory (NPSI) and Brief Pain Inventory (BPI). 4. Assessment of mood on Depression, Anxiety and Positive Outlook Scale (DAPOS), and assessment of sleep on MOS Sleep Problem Index (SPI) scale. 5. Intraepidermal nerve fiber density and length of a 3-mm skin punch biopsy. 
Testing for intervention response (repetitive testing):
 
 1. Daily average and maximum pain intensity recording on 0-10 NRS; 2. Scoring of NPSI, BPI, DAPOS and SPI questionnaires at the end of week 4
Statistical Methodology	
The primary outcome is the comparison of slopes of the two correlations: baseline MPT vs % pain reduction with pregabalin, and baseline MPT vs % pain reduction with placebo. The two slopes will be compared using t-test. Significant difference between slopes will indicate that baseline MPT correlates with pregabalin response (vs. placebo response) in painful CIPN.
 
As secondary analyses, we will compare mean absolute pain reduction with pregabalin to absolute pain reduction to placebo (both for average daily pain and maximum daily pain), using paired t-test, given normal data distribution. If normal distribution is not obtained, we will use Wilcoxon signed ranked test.
 
In addition, we will perform Fisher exact test to compare the proportion of patients with 50% or more reduction in average pain intensity from baseline with pregabalin vs. placebo. Number needed to treat (NNT) will be calculated from this proportion of responders to pregabalin and placebo.

Table of Contents

1. SYNOPSIS	2
2. STUDY PROTOCOL	6
2.1 Background and Significance	6
2.2 Objective.....	8
2.3 Patient Selection	8
2.3.1 Inclusion Criteria	8
2.3.2 Exclusion Criteria	8
2.4 Design and Procedures.....	9
2.4.1 Study Design.....	9
2.4.2 Pre-Study Period	10
2.4.3 Study Period.....	11
2.4.4 Minimization of Bias	14
2.4.5 Observations and Measurements	15
2.4.6 QST protocol.....	15
2.4.7 Statistical Methods.....	17
2.4.8 Sample Size.....	18
2.4.9. Dealing with missing data.....	18
2.4.10 Clinical Procedures and Laboratory Tests	18
2.4.11 Drug procurement and storage.....	19
3.0 MANAGEMENT OF INTERCURRENT EVENTS	19
3.1 Adverse Experiences.....	19
3.2 Premature Discontinuation	21
3.3 Potential Risks	21
3.4 Procedures to Minimize Potential Risks.....	22

2. STUDY PROTOCOL

2.1 Background and Significance

Chemotherapy-induced peripheral neuropathy (CIPN) affects 25-90% of patients treated with anticancer drugs such as platinum compounds, taxanes, and vinca alkaloids, or their combinations. CIPN can be early-onset or late-onset, and its prevalence and severity are affected by age, single chemotherapy dose intensity, cumulative dose, length of therapy, and other factors (Chaudhry, Rowinsky et al. 1994, Polomano and Bennett 2001). The early onset neuropathy associated with chemotherapy is frequently a dose-limiting side effect of these drugs, hindering the ability to achieve high effective doses. Indeed, patients developing CIPN eventually receive lower cumulative doses of chemotherapy (Eckhoff, Knoop et al. 2013, Speck, Sammel et al. 2013) which can increase the rate of anticancer treatment failure. The early-onset neuropathy may transition into a chronic condition, or late-onset neuropathy can appear 2-8 weeks after chemotherapy discontinuation. Some of the patients affected by chronic neuropathy are in remission or cancer-free, and could otherwise be fully functional, yet painful CIPN causes substantial suffering and significantly reduces their quality of life (Hershman, Weimer et al. 2011).

Painful CIPN, as clinical experience and research data suggest, is rather treatment-resistant, and is more challenging to treat compared to other neuropathic pain conditions. Illustrating this challenge is the fact that only one large positive randomized controlled study on the treatment of CIPN has been published (among more than 300 randomized controlled pharmacotherapy trials in various neuropathic pain conditions), demonstrating effectiveness of duloxetine, a serotonin norepinephrine reuptake inhibitor. In a trial of 231 patients with taxane- or paclitaxel-induced CIPN, patients were randomized to treatment with duloxetine 60 mg/day or matching placebo for 5 weeks. The average decrease in pain intensity was greater with duloxetine than with placebo (Smith, Pang et al. 2013). Venlafaxine, another SNRI, has shown efficacy in the possible prevention of oxaliplatin-induced PN, when administered for 10 days after onset of acute neurotoxicity (Durand, Deplanque et al. 2012).

The mechanisms of nerve injury in CIPN, and the transition from acute to chronic phase of neurotoxicity, are not fully understood. The patients present with peripheral nerve fiber degeneration and hyperexcitability, and one of the leading theories regarding the causation is related to the mitotoxic effects of chemotherapy on somatosensory afferent neurons. Despite differences in mechanisms of action, the different chemotherapy agents share some of the pathological findings in CIPN, e.g. common final pathway of axonal mitochondria damage. In addition, preclinical data suggest that CIPN caused by oxaliplatin and taxanes (paclitaxel and docetaxel) results in overexpression of $\alpha 2\delta$ subunits of voltage-gated Ca^{2+} channels in the dorsal root ganglion (DRG) and spinal cord dorsal horn in rats. This may imply that modulating neuronal Ca^{2+} channel function by $\alpha 2\delta$ ligands may be effective in treating CIPN caused by oxaliplatin and taxane compounds. Indeed, in preclinical studies administration of gabapentin (Lynch, Wade et al. 2004, Ling, Authier et al. 2007, Xiao, Boroujerdi et al. 2007) and pregabalin (Peng, Xi et al. 2012, Aoki, Kurauchi et al. 2014) has been demonstrated to successfully reduce mechanical and thermal hypersensitivity in rat models of CIPN induced by these compounds. Although CIPN induced by different drugs may result in a similar symptom pattern, the underlying mechanisms may vary. In mice, treatment with paclitaxel and oxaliplatin increases the DRG expression of $\alpha 2\delta$ mRNA, while treatment with vincristine does not result in similar changes. In addition, treatment with $\alpha 2\delta$ subunit ligand gabapentin was effective in mice with paclitaxel and oxaliplatin-induced mechanical allodynia, but not in vincristine-induced mechanical allodynia (Gauchan, Andoh et al. 2009). Thus, preclinical data suggests that $\alpha 2\delta$ subunit

of voltage-gated Ca^{2+} channels is a promising target for attenuating oxaliplatin- and taxane- induced CIPN.

Neuronal voltage-gated Ca^{2+} channels as a therapeutic target for treating CIPN remain largely unexplored clinically. Recently published guidelines on CIPN failed to identify any treatment for which robust data exist to support clinical effectiveness (Hershman, Lacchetti et al. 2014). Studies with first-line agents for neuropathic pain treatment, such as gabapentin or tricyclic antidepressants, yielded negative or inconclusive results, and serotonin norepinephrine reuptake inhibitor duloxetine is the only drug for which positive results from a large randomized controlled trial are available. The only published randomized clinical trial assessing effectiveness of an $\alpha 2\delta$ ligand gabapentin in CIPN was negative (Rao, Michalak et al. 2007), but it is important to note that patients in this study did not necessarily have pain as inclusion criterion, and these methodological issues may have affected the analgesic outcomes. Recent observational data suggest clinical effectiveness of pregabalin in oxaliplatin- and taxane-induced peripheral neuropathy (Nihei, Sato et al. 2013). Twenty seven patients with oxaliplatin-induced PN, and 28 patients with paclitaxel-induced PN treated with pregabalin were compared to 20 and 25 patients (respectively) treated with other treatments, such as amitriptyline, carbamazepine, clonazepam and vitamin B12. Response rates in both CIPN groups were better in pregabalin-treated subjects than in non-pregabalin treated subjects (40.7% vs 10.0% experienced decrease in neuropathy grade in oxaliplatin-induced PN; 28.6% vs. 12.0% experienced decrease in neuropathy grade in paclitaxel-induced PN). There is an urgent need to find efficacious treatment options for patients suffering from painful CIPN. In neuropathic pain conditions in general, the “one size fits all” pharmacotherapy approach does not seem particularly effective, and the current trend is to move toward more innovative subgroup response and responder analysis methods. Numbers of patients needed to treat (NNT) to achieve substantial pain relief (e.g. $\geq 50\%$) compared to placebo in neuropathic pain are between 4 and 7 for most drugs, which is discouraging. However, some data, mainly from ad-hoc analyses of clinical trials, suggest that subgroups of patients with neuropathic pain identified by somatosensory phenotyping, may be more responsive to specific treatments (Campbell, Kipnes et al. 2012, Yarnitsky, Granot et al. 2012, Haroutiunian, Nikolajsen et al. 2013). For example, in an HIV sensory neuropathy study that was negative overall, a subgroup of patients with mechanical allodynia (excessive pain response to pin-prick stimulation) at baseline had a better analgesic response to pregabalin treatment than to placebo (Simpson, Schifitto et al. 2010).

Pregabalin (Lyrica[®]) is a voltage-gated calcium channel $\alpha 2\delta$ subunit ligand that has shown efficacy in numerous trials of neuropathic pain conditions. It is currently approved by the FDA for the treatment of several neuropathic pain conditions, including pain associated with diabetic peripheral neuropathy, postherpetic neuralgia, and spinal cord injury. It is also approved for the treatment of fibromyalgia (Lyrica Prescribing Information). The NNT for pregabalin in various neuropathic pain conditions is 7.7, and it is generally safer than the SNRIs in treating neuropathic pain, with a number of patients needed to treat for 1 patient to drop out of study due to adverse effects (NNH) of 13.9 for pregabalin, compared with 11.8 for SNRIs (Finnerup, Attal et al. 2015). The FDA-approved maximal dose of pregabalin is 600mg/day.

Some animal data supports the effectiveness of pregabalin on mechanical allodynia in chemotherapy-induced or other neuropathies (Hahm, Ahn et al. 2012, Miyazaki and Yamamoto 2012, Aoki, Kurauchi et al. 2014).

Based on the findings of pin-prick hypersensitivity as predictor of response to pregabalin, together with animal data and preliminary clinical data supporting pregabalin efficacy in CIPN, we hypothesize, that increased mechanical hypersensitivity to pinprick (lower mechanical pain threshold - MPT) corresponds to better analgesic response to pregabalin treatment in painful CIPN.

2.2 Objective

The primary objective of the proposed study is to determine the correlation between baseline mechanical pain threshold (MPT) and analgesic response (% pain reduction) after 4-weeks of treatment with pregabalin vs. placebo in patients with painful peripheral neuropathy induced by oxaliplatin, paclitaxel, and/or docetaxel.

The additional aims of the study are:

1. To investigate whether treatment with pregabalin results in better pain relief compared with placebo in patients with painful CIPN.
2. To identify additional phenotypic predictors of response to pregabalin in CIPN by performing comprehensive baseline somatosensory phenotyping.

2.3 Patient Selection

Thirty-five evaluable patients with painful CIPN will be recruited from the Siteman Cancer Center and the Pain Management Center of Washington University in St. Louis.

2.3.1 Inclusion Criteria

Inclusion criteria:

1. Age >18
2. Distal symmetric pain distribution (both feet, with or without pain in hands).
3. Pain appeared during or up to 12 weeks after treatment with oxaliplatin, paclitaxel, docetaxel or any combination of these.
4. Score of 4 or more on DN4 neuropathic pain questionnaire (Bouhassira, Attal et al. 2005).
5. Pain duration > 2 months.
6. Patient report of average daily pain intensity >3 on 0-10 Numerical Rating Scale (NRS) in the past week.
7. Women of childbearing potential and men must agree to use adequate contraception (hormonal or barrier method of birth control, abstinence) prior to study entry and for the duration of study participation. Should a woman become pregnant or suspect she is pregnant while participating in this study, she must inform her treating physician immediately.
8. Able and willing to sign an IRB-approved written informed consent.

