2.4 Design and Procedures

2.4.1 Study Design

This is a prospective, randomized, double-blind, placebo-controlled, cross-over pilot study in 35 evaluable subjects with painful CIPN. If our hypothesis is confirmed, then patients with lower MPT at baseline will have larger analgesic effect with pregabalin than with placebo.

Registration, Randomization, and Blinding

Subjects that meet all criteria and wish to participate will be assigned study ID # and be randomized for the sequence of treatment for the study sessions. Patients may not start any protocol intervention until registration through the Siteman Cancer Center (SCC) is complete. The following steps will be taken before any study interventions occur: 1) confirmation of patient eligibility, 2) registration of patient in the SCC database, and 3) assignment of study ID #.

According to a computer-generated list of randomization numbers, the sequence of interventions will be determined: pregabalin and then matching placebo, or vice versa. Randomization will be performed by blocks of 8 subjects, without stratification. An unblinded

investigator will be assigned to match the study number with randomized treatment sequence, and this person will dispense the study medications. This investigator will not be involved at any stage at patient assessment, data collection or analysis. The participants and all other study personnel will be blinded to the treatment sequence allocation. At the end of the study, the subjects will be asked to complete a participant blinding questionnaire, to assess the risk of possible unmasking. As an additional approach to identify inadvertent failure in randomization or patient allocation, a single blood sample will be obtained at the last visit of each session, to determine the presence of pregabalin in plasma in patients allocated to pregabalin, and lack of drug in the placebo arm.

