2.4.3 Study Period

[figure not shown]
The cross-over study design and the treatment plan are illustrated in Figure 1. Pregabalin (or matching placebo) will be administered for four weeks in each period. The target dose will be increased from 75mg BID to 300mg BID within 7 days (per schedule in Fig. 1), and continued for an additional 22 days.

In case of any grade 2 adverse events (Common Terminology Criteria for Adverse Events – CTCAE version 4.0), the dose will be reduced to the last dose prior to dose increase (i.e. to 150mg BID from 300mg BID; to 75mg BID from 150mg BID). If the adverse effect diminishes to \leq Grade 1, one attempt to dose escalate will be allowed after 3 additional days. If the dose escalation is not tolerated (i.e. recurrent grade 2 adverse event), the treatment will be continued at the previous (lower) dose until day 28. Any CTCAE \geq grade 3 will trigger subject withdrawal from the study.

At the end of treatment sequence, the dose will be tapered over 3 days (e.g., 150mg BID for 2 days, then 75 mg BID for 1 additional day) followed by 10 days of study drug-free washout (end of week 6). In subjects with CrCL 30-60 mL/min, the target (maximum) dose will be 300mg/day. In these subjects the dose will be tapered over 3 days of 75mg BID dosing. If subject's highest tolerable maintenance dose was 75mg BID, the taper schedule will be 75mg QD over 3 days.

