The subjects will return on day 28 ± 2 days [prior to washout period] for Visit 2 to turn in the 4 questionnaires which were completed on day 28 (week 4a), sensory mapping, PK blood sample and a blood sample for renal and hepatic function tests will be obtained. After the washout period (end of week 6), the subjects will return to Washington University Medical Center for Visit 3, prior to second treatment sequence. The subjects will undergo QST and CPM procedures (Fig. 1), and complete the appropriate questionnaires (SPI, NPSI, BPI, DAPOS). Thereafter, the second 4-week treatment sequence will be scheduled for weeks 7-10, according to the same titration schedule as sequence 1. Three day dose tapering-down will be practiced at the end of second treatment sequence in the same manner as was performed for the first treatment. The subjects will return for the final assessment visit [Visit 4] approximately 3 days after end of week 10 (end of 3-day taper). Safety and efficacy data, a PK blood sample and a blood sample for renal and hepatic function tests will be obtained, turn in 4 questionnaires which were completed on day 28 (week 4b), sensory mapping, and the optional skin biopsy in subjects who agreed, will be obtained at Visit 4.

Figure 1.

Legend: BPI – brief pain inventory; NPSI – neuropathic pain symptom inventory; DAPOS – depression, anxiety and positive outlook scale; SPI – sleep problem index; QST – quantitative sensory testing; CPM – conditioned pain modulation. Tx – treatment.

Rescue Analgesia

Study subjects will be allowed to take oral acetaminophen (paracetamol) as rescue analgesic at a dose of 1 gram up to 4 times/day. FDA-approved 500mg acetaminophen tablets will be purchased and provided by the investigators. If the patient has been receiving PRN short-acting opioids (with or without acetaminophen) for non-CIPN pain, up to 4 daily doses will be allowed during the study, with daily recording of analgesic consumption. The total amount of acetaminophen (from opioid-acetaminophen combination and PRN acetaminophen alone) will not exceed 4 grams/day. In subjects with liver disease (AST or ALT increased, but less than 3 times the upper normal level), the total daily dose of acetaminophen will be limited to 2 grams. Based on these considerations, each patient will receive individual written instructions regarding PRN analgesic use, and will be required to report it appropriately.

Outcomes Assessment:

Clinical Efficacy

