Patients will complete an electronic diary with daily report of their average and maximum daily pain intensity, recorded every evening before bedtime. The percentage of pain reduction for primary outcome will be assessed from the difference between baseline average pain intensity and the average pain intensity of last 5 days of treatment (day 24-28), on 0-10 NRS.

Secondary efficacy outcomes will include: 1) The difference between baseline maximum pain intensity and the maximum pain intensity of the last 5 days of treatment, on 0-10 NRS; 2) The proportion of patients achieving 50% or more pain relief with pregabalin vs. placebo treatment; 3) Difference in Pain Severity and Pain Interference scales of the BPI, assessed at baseline and day 28 of treatment. The daily use of rescue analgesia (oral acetaminophen) will also be recorded.

Table 1. Data assessment schedule

Required Assessments	Screening and Enrollment Baseline Visit	Week 1a	Week 2a	Week 3a	Week 4a	End of Treatment A (Day 28 +/- 2)	Wash-out	Study crossover visit	Week 1b	Week 2b	Week 3b	Week 4b	End of Study Visit (Day 30 +/- 3)
Study visits	Visit1 (a/b)*					Visit2		Visit3					Visit 4
Informed consent	✓												
Pregnancy (urine Hbhcg) test for women	✓												
Comprehensive Metabolic Panel (CMP) blood test**	✓					✓							✓
Inclusion/exclusion criteria	✓												
Randomization	✓												
Demographic data collection	✓												
Sensory Mapping	✓					✓		✓					✓
BPI questionnaire	✓				✓			✓				✓	
NPSI questionnaire	✓				✓			✓				✓	
DAPOS questionnaire	✓				✓			✓				✓	
SPI questionnaire	✓				✓			✓				✓	
QST	✓							✓					
CPM	✓							✓					
Dispense study drug	✓							✓					
Pain intensity 0-10 NRS	✓	daily	daily	daily	daily			✓	daily	daily	daily	daily	✓
Adverse Event assessment		daily	daily	daily	daily				daily	daily	daily	daily	✓
Telephone communication		weekly	weekly	weekly	weekly				weekly	weekly	weekly	weekly	
Blinding questionnaire***		✓											
Pill count								✓					✓
Blood sample (PK)						✓							✓
Skin biopsy (optional)													✓

*Visit 1 may be conducted over 2 visits to complete all assessments if required for subject tolerability or convenience

** A blood sample for CMP will not be obtained if recent (<30 days) results are available.

*** Blinding questionnaire to be administered via EMA device on Day 5 of study drug treatment

Subject Blinding Perception

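### On-study pregnancy notice names only the treating physician, and no pregnancy test is scheduled before the second dispensing; a cheap, low-priority safety edit closes both

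*Combined protocol and SAP*

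**What the plan says.** **Notice.** Item 7 of 2.3.1 requires contraception throughout participation and then adds: "Should a woman become pregnant or suspect she is pregnant while participating in this study, she must inform her treating physician immediately". The protocol does not define who that physician is. Item 7 in the synopsis has the contraception duty but not the notice duty; it runs straight on to the consent criterion: "prior to study entry and for the duration of study participation. 8. Able and willing to sign".

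**Testing.** The row "Pregnancy (urine Hbhcg) test for women" in Table 1 (section 2.4.3) has a single tick, at the screening and baseline visit. Sections 3.4 and 4.2 also describe one test.

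**Dispensing.** Table 1 has two dispensing ticks, at Visit 1 and at the crossover visit (Visit 3). Section 2.4.1 gives the two sequences as "pregabalin and then matching placebo, or vice versa". Section 2.4.3 places the return "for Visit 3, prior to second treatment sequence", after a 3-day taper "followed by 10 days of study drug-free washout (end of week 6").

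**Related rules.** Pregnancy is an exclusion at entry (2.3.2, item 9). The withdrawal list in 3.2 does not name it, but does allow withdrawal when the investigator judges it best for the participant.

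**The concern.** Pregnancy bars entry and contraception is required throughout, so the plan already treats pregnancy as incompatible with dosing. It verifies this once. A woman who follows item 7 to the letter may have told only someone who does not control the study drug. Nothing listed for Visit 3 tests for pregnancy or asks about it before drug is handed over.

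This matters most in the placebo-first sequence, about half of the participants, for whom Visit 3 precedes the first pregabalin dose. Section 4.5 makes women of childbearing potential eligible and expects most participants to be women, so the affected group is not empty by design. What is at stake is an avoidable drug exposure in an unrecognized or unreported pregnancy. No inferential result is at stake.

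**Working it through.** **1. Timing of Visit 3.** The plan puts Visit 3 at the end of week 6, which is 6 × 7 = 42 days. The components in 2.4.3 and the synopsis give the same:

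- four-week period + taper + drug-free washout: 28 + 3 + 10 = 41 days
- titration wording (7 days, then 22 more) + taper + washout: 7 + 22 + 3 + 10 = 42 days
- synopsis, 4 weeks + 2 weeks: 28 + 14 = 42 days

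**2. Age of the only scheduled test at second dispensing.** Age = days from test to first dose + days from first dose to Visit 3.

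| Case | Age at Visit 3 |
|---|---|
| Same-day test, period 1 completed | 41 to 42 days |
| Period 1 ending at the edges of the Visit 2 window (day 26 or 30) | 26 + 13 = 39 to 30 + 13 = 43 days |
| Visit 1 split over two visits (Table 1 footnote) | older, by an unstated number of days |
| Early stop, e.g. day 7, then the 2-week washout in 3.2 | 7 + 14 = 21 days |

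With a test at Visit 3 the age becomes 0 days, and scheduled tests rise from 1 to 2 per woman.

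**3. What follows Visit 3.** Period 2 with taper is 28 + 3 = 31 days, or 7 + 22 + 3 = 32 days, of study drug. This is pregabalin in the placebo-first sequence.

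**4. Is there another pregnancy-specific check before period 2?** The routes in the text are:

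- weekly telephone contact (2.4.3, Compliance; 3.3.1)
- the daily diary, reviewed about weekly (2.4.3, Electronic data collection; 3.3.1)
- contact with the PI or coordinator about any adverse event (2.4.3, Safety)
- their pager number with the study drug prescription (2.4.11)
- the duty to report potentially serious adverse effects to the study team (3.1)
- best-interest withdrawal (3.2)

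All lead to study staff. None mentions pregnancy, and it is not among the seven prompted adverse events in 3.1.

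**5. Order of magnitude (assumed inputs only).** The documents do not give the number of women of childbearing potential or a pregnancy rate. Assume 2 to 15 such women among 35, and a 0.1% to 1% chance of pregnancy over six weeks on contraception.

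- Expected pregnancies by Visit 3: 2 × 0.001 = 0.002 to 15 × 0.01 = 0.15
- Placebo-first half: 0.001 to 0.075
- Unknown to the team at Visit 3, assuming 10% to 50%: 0.001 × 0.1 = 0.0001 to 0.075 × 0.5 = 0.0375

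The top of the range, about 1 in 27 trials of this size (1 / 0.0375 = 26.7), needs all three upper assumptions at once. A urine test would also miss the most recent conceptions, so the benefit is smaller than these figures.

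**The case against.** **The notice may be settled elsewhere.** The consent form is the natural place to tell a participant whom to call, and it was not available for review. Nor were the funder's Safety Reporting Reference Manual (3.1) or the appended prescribing information (3.1). This stands. A reader might infer that the trial has no route for a pregnancy to reach the study team; the documents do not support that. If the unseen documents name the team or require a retest, the change is only to bring item 7 and Table 1 into line.

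**The treating physician may be study staff.** Participants come mainly from the same institution's cancer and pain clinics, and the co-investigator is an oncologist. They also come by referral and through flyers (4.3). The text does not settle the question, so it is unsafe to infer that the recipient is outside the trial.

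**Staff contact is frequent.** This also stands, and it is the main reason why the priority is low. A reader might infer an unsupervised stretch before Visit 3, because the rows "Adverse Event assessment" and "Telephone communication" are empty at end of treatment A, washout and the crossover visit. That reading is too strong. The interval has face-to-face visits at both ends, 3.1 says that the daily prompts run through the study period, and an empty cell does not show that staff ask nothing.

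**No rule is breached.** Correct. The 30-day limit on reusing laboratory results applies to the metabolic panel; a reader might take it as a standard for the pregnancy test, but the plan does not say so. The pregabalin risk list in 3.3.1 names no reproductive risk, so the severity of an exposure cannot be sized from these documents.

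**Conclusion.** The point holds for the supplied protocol as a minor, optional safety improvement. Two facts support it: item 7 names only an undefined treating physician, and the one scheduled pregnancy test precedes the first of two dispensings. The age of about 41 to 42 days assumes a same-day test and a completed first period; it should not be read as applying to every participant.

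The event estimate rests wholly on assumed inputs and shows only that expected cases are very few. That most participants are expected to be women says nothing about how many could become pregnant. Randomization, sample size and the primary slope comparison do not depend on this point.

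**What to change.** 1. **Item 7 in 2.3.1, and its synopsis counterpart:** require a woman who is or may be pregnant to tell the study team (PI or study coordinator) at once, as well as her treating physician. Align the consent form if it does not already say so.
2. **Table 1:** add a urine pregnancy test at Visit 3 for women of childbearing potential, with the result known before study drug is dispensed.

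Optionally, 3.2 could state that a confirmed pregnancy stops study drug (with taper) and that no second period is started.

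**Cost:** one sentence in each place, one tick in Table 1, and one extra urine test per such woman at a visit that already takes place. The downside is that test and possibly a rare withdrawal from the 35 evaluable participants.
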